1.5.3 Feasibility and Pilot data

The two above-mentioned RCTs show that patients with PDPN can be randomised to FREMS vs sham FREMS, and that FREMS overall is efficacious in reducing pain and improving QoL in PDPN. Below we share 3 sets of data concerning the use of FREMS in routine care from the UK and the Netherlands and a pilot RCT using FREMS as a third line treatment modality.

1.5.4 Routine care data from Birmingham Heartlands Hospital, UK

Birmingham Heartlands Hospital has an established diabetes-related neuropathy clinic since 2012; some of the patients in this clinic have PDPN. The APTIVA FREMS unit was given to this clinic by BHR Pharmaceutical Ltd, who also covered the cost of the consumables. Patients with PDPN (N=23) who failed to respond to (or did not tolerate) at least two lines of pharmacotherapy (including the drugs recommended by NICE guidance) were offered FREMS. FREMS was delivered in the diabetes centre by a health care assistant over 10 consecutive out-patients sessions (excluding weekends) for 35 minutes each. Patients with contraindications to FREMS (e.g. epilepsy, implantable device) were excluded.

By 3 months, pain NRS and EQ-5D-5L VAS improved from mean±SD 8.4±1.4 to 6.2±3.0 and 57.5±10.6 to 72.5±3.5 respectively, which was maintained by 6 months. All 12 patients who were on opioids at baseline stopped them. Despite the lack of reimbursement for travel, none of the patients declined FREMS or missed any sessions (unpublished data).

1.5.5 Uncontrolled data from the Netherlands

These data are from Elisabeth-Tweesteden Hospital, Tilburg and Bethesda Diabetes Research Centre, Hoozeveen. This was an uncontrolled prospective study of patients with PDPN and persistent pain despite at least two lines of pharmacotherapy (including pregabalin or duloxetine or similar as per NICE guideline). The primary outcome was 50% reduction in pain scores at 1 and/or 3 months post-FREMS. In responders, FREMS was repeated every 4 months up to 12 months. FREMS was applied to both legs below the knees using 4 sets of electrodes per leg; the treatment consisted of 10 sessions of 35 minutes given over 14 days. Pain was assessed using the Neuropathic Pain Symptom Inventory (NPSI) and QoL was assessed using the EQ-5D-5L.

248 patients met the inclusion criteria; 56% male, average age 65 years old, and average diabetes duration 12.6 years. Before FREMS treatment, the average NPSI was 50±18. This improved after 1 and 3 months to 34±20 and 32±20 respectively ($p<0.001$ vs baseline). This improvement was maintained at 12 months ($p<0.001$). 50% decreases in NPSI scores (which is considered the ideal response) were seen in 80/248 (32.2%) at month 1 and in 87/248 (35.1%) at month 3. One third reduction in pain scores (which is considered clinically meaningful) occurred in 111 (44.8%) patients at month 1, and 123 (49.6%) at month 3.

The EQ-5D-5L VAS improved from 52.6±15.9 to 62.8±14.6 and 63.6±16.7% at months 1 and 3 respectively ($P<0.001$ vs baseline).

All of these improvements in pain scores, QoL and disability scores occurred in the context of a reduction of neuropathic pain medications over a 12 month period, including stopping opioids (unpublished data under peer review).

1.5.6 A single centre pilot RCT in Nuneaton, UK: The FREMS-TOP study [66]

This study aimed to randomise 35 patients; but recruitment was stopped early in April 2020 due to the COVID-19 pandemic. At closure, the study had randomised 25 patients and 22 had completed the study. This RCT included adults with either type 1 or type 2 DM, with neuropathic pain score ≥ 4 pain on NRS at screening and at randomisation despite receiving at least 2 of the below mentioned treatment options: duloxetine, pregabalin, gabapentin, amitriptyline, carbamazepine, phenytoin, tramadol, opioids. This RCT population is therefore similar to the population proposed in this protocol. Patients were randomised to FREMS + standard care vs standard care only. FREMS was delivered for 35 minutes/day for 10 days over 2 weeks excluding weekends.

Results: Over the 3 months follow up, patients randomised to FREMS + standard care had improvements in pain severity (based on SF-MPQ-2 and DN-4 questionnaire), QoL and insomnia, while patients randomised to standard care had no improvement in pain severity or insomnia and had worsening of QoL. Similarly, at 3 months the Patient Global Impression of Change (PGIC) at 3 months was greater in the intervention group compared to the controls ($r=0.75$, $p=0.005$).

1.5.7 Summary of the presented evidence

Taken together, the two published RCTs show that FREMS can reduce pain and improve QoL in patients with PDPN compared to sham FREMS, although these studies were small and included a wide range of patients with PDPN including those with mild disease which makes it difficult to determine where FREMS treatment can be used best (i.e. early vs late in the course of treatment). The two RCTs and pilot RCT show that recruitment and randomisation are feasible. The two health service evaluations show that FREMS is acceptable to patients with PDPN who fail to respond to two classes of medications as recommended by NICE, and that FREMS is associated with improvement in pain and QoL for up to 12 months in a real-life setting. The pilot RCT shows that FREMS is potentially beneficial in patients with PDPN as a third (or above) line treatment. All the studies and health service evaluations showed that the improvement in pain and QoL occurred in the context of a reduction in neuropathic pain medication including opioids.

1.6. Justification for choice of control arm

The control in this trial will be low intensity high frequency conventional TENS delivered in the same manner as FREMS (35 minutes for 10 days) using the same electrodes and device to the lower legs. TENS was chosen for multiple reasons:

1. Blinding:

To enable a blinded study to be undertaken. Please see Section 6.7.

2. TENS effects uncertain and short lived in PDPN:

A 2017 Cochrane systematic review in adults concluded that the effects of TENS in neuropathic pain were unclear due to the very low quality of evidence [33]. There were only two RCTs in PDPN in this systematic review [34, 35]. The RCT by Nabi et al delivered TENS to the lower limbs for 10 sessions, of 20 minutes each [36]. This RCT showed that the pain score based on NRS improved by 1 week but **returned to baseline by 3 months** post-treatment [36]; these results were similar to an older meta-analysis in patients with PDPN [35]. Other RCTs and systematic reviews also showed no effects for TENS in PDPN [35, 37]. Since the publication of the Cochrane review, another RCT has been published; it only included 5 patients with a study duration of 10 days [38]. In this RCT, the investigators used a cross-over design with a 1-week washout period which they considered to be enough in order not to have residual effects from TENS [38]. Hence, TENS is unlikely to produce meaningful reductions in pain scores by the primary outcome at 3 months and study end at 6 months considering the rapid onset and offset of conventional low intensity TENS [39].

Why low intensity high frequency TENS rather than other TENS types?

Low-intensity, high-frequency TENS (conventional TENS) at the site of pain produces “strong but comfortable TENS paraesthesia” [39]. This selectively activates large diameter non-noxious afferents to elicit segmental analgesia [39]. The mechanism of action results in rapid onset and offset of effects requiring TENS to be used whenever needed to achieve pain relief (even throughout the day) [40]. On the other hand, FREMS effects are likely to be due to improved endothelial function and microvascular flow, increased vascular endothelial growth factor and improvements in several aspects of neuropathy as detailed in Section 1.4.2 below [41-44]. These differences in mechanisms are the likely cause for the different duration in pain relief and extended carry over effect from FREMS. Hence the use of conventional low intensity high frequency TENS is unlikely to affect the study outcomes and at the same time will aid blinding.

1.7. Justification of choice of primary outcome

The primary outcome is the difference in the 7-day mean 24-hour pain score (evaluated at participant level) on an 11-point NRS scale (0 = no pain and 10 = worst pain imaginable) between arms measured at 3 months post randomisation. The 7-day mean 24-hour NRS is considered the gold standard for the assessment of neuropathic pain and has been employed in almost all well-designed neuropathic pain studies over the past 10 years [45-47]. Changes in the 7-day mean NRS were used by the international IMMPACT recommendations and others to determine and validate the clinically important differences in pain intensity [45, 48]. IMMPACT is the Initiative on Methods, Measurement, and Pain Assessment in Clinical Trials, which included a consensus statement from 40 participants from universities, governmental agencies, a patient organisation, and the pharmaceutical industry.

NICE clinical guidance 173 also recommended the use of the 11-point NRS in neuropathic pain trials in the research recommendations section. The European Medicine Agency also recommends the use of the NRS in pain trials [49]. The NRS will be collected daily throughout the study period via text messages or via email (as suggested by the PPI group), but only the average of the 7 days prior to the 3 months-time point will be used for the primary outcome analysis. The NRS daily pain score will be facilitated by the University of Birmingham’s ReDCAP system via either email or the third-party text message provider FireText.

We chose the primary outcome to be at 3 months with a longer follow up at 6 months as this is consistent with other trials in the field of PDPN which were between 6-12 weeks duration [32, 50-55]. The previous FREMS RCTs, the health service evaluations, the pilot RCTs, and our clinical experience with using the device suggests that the treatment effect starts wearing off around 4-6 months after the initial FREMS treatment. In our clinical experience, patients contact us asking for another FREMS treatment session 4-6 months after their initial treatment. The Outcome measures of Rheumatology OMERCAT-12 recommended using 6 months follow up as minimal duration in chronic pain trials [56].

2. AIMS AND OBJECTIVES

2.1 Internal pilot objectives

1. To assess the feasibility of identifying eligible patients.
2. To assess the acceptability of randomisation to receive the intervention or not.
3. To determine if the pilot phase should continue to a full trial.

The stop/go criteria will be assessed after 6 months of recruitment. This is described in detail in section 8.1.

2.2 Main trial objectives

2.2.1 Clinical objectives

1. To evaluate the efficacy of FREMS using 11-point NRS 24-hour pain scores (0 to 10) averaged over the last 7 days before the 3 months follow up assessment (Primary objective).
2. To evaluate the impact of FREMS on other efficacy outcomes including sleep, QoL, mood and medication use at the 3 months follow up assessment.

2.2.2 Economic objectives

To evaluate the cost-effectiveness of FREMS in patients with PDPN.

2.2.3 Safety objectives

To describe (Serious) Adverse Events data (summarised both at patient level and event level).

2.2.4 Subgroup study objectives (exploratory objectives)

To conduct a subgroup analysis to investigate if patient phenotypes (demography, diabetes type, type of pain, mood, sleep and quantitative sensory testing profiles) predict response to treatment.

3. TRIAL DESIGN AND SETTING

FREMS-PDPN is a pragmatic, multi-centre, 2-arm, parallel group, double blind, sham controlled, randomised trial of patients with PDPN (defined as pain severity of ≥ 4 on 11-point numerical rating scale [NRS] measuring 24-hour pain scores [0 to 10] averaged over the last 7 days) who have not responded to at least two different classes of neuropathic pain medications as per NICE guidance.

The trial will have an internal pilot phase with stop/go criteria as described in section 8.1. The patients will be randomised in a 1:1 ratio to either FREMS + standard care or TENS + standard care. The primary outcome (24-hour pain NRS averaged over the last 7 days) is measured post-randomisation at 3 months and the final follow up is at 6 months post-randomisation. The administering team, the participant and the researchers will be blinded to treatment allocation.

Patients will be recruited from NHS Trusts that have PDPN services and the aligned primary care and podiatry services, as well as social media and Diabetes UK local patient groups. The study device delivering both FREMS and TENS will be placed in the Trusts at secondary care sites.

3.1 Safety and mechanistic sub-study

This sub-study is aimed at ensuring that there is no worsening sensory dysfunction with the trial interventions. The sub-study will also look for different responder rates in relation to the quantitative sensory testing (QST) phenotype. The sub-study will perform QST using the validated and standardised German Research Network on Neuropathic Pain (DFNS) protocol, which also has validated age and gender at birth normative values [67]. The DFNS has been shown to have good inter-observer and test-retest reliability for use in patients with sensory disturbances of different aetiologies to help identify mechanisms of neuropathic pain [68]. The DFNS protocol takes 60 minutes to perform and, in this trial, will only be conducted in two trial centres, Sheffield and Liverpool, as the Principal Investigators (PIs) in these centres have already been trained in the DFNS protocol. The DFNS will be performed at baseline, 3 months and 6 months. This sub-study will ensure the safety of FREMS treatment by examining any changes in QST (including sensory perception of sharp, cold, warm, or vibration stimuli) during the trial as performed in previous trials [69].

3.2 Assessment of risk

All clinical trials can be considered to involve an element of risk and in accordance with the Birmingham Clinical Trials Unit (BCTU) standard operating procedures this trial has been risk assessed to clarify any risks relating uniquely to this trial beyond that associated with usual care. A Risk Assessment has been conducted and concluded that this trial corresponds to the following categorisation: No higher than the risk of standard medical care.

4. ELIGIBILITY

4.1 Inclusion criteria

1. Aged ≥ 18 years.
2. Neuropathic pain affecting both feet for ≥ 3 months or taking pain medication for neuropathic pain for ≥ 3 months.
3. Mean pain score ≥ 4 on the daily NRS for one week prior to randomisation.
4. Douleur Neuropathique 4 (DN-4) questionnaire score $\geq 4/10$ at screening to confirm the diagnosis of bilateral distal symmetrical neuropathic pain [70].
5. Diabetes-related neuropathy based on the Michigan Neuropathy Screening Instrument (MNSI) (MNSI questionnaire scored ≥ 7 or examination scored >2) [71, 72].
6. HbA1c <108 mmol/mol or 12% taken (within last 2 months).
7. Have tried at least two drugs from two different classes for PDPN.
8. Willing and able to comply with the study schedule and be available for the treatment duration.
9. Able to give written informed consent.

4.2 Exclusion criteria

1. Non-diabetic neuropathies.
2. Currently using TENS for PDPN.
3. History of epilepsy.
4. Other painful medical conditions where the pain is significantly more severe than their PDPN pain (patients will not be excluded if the pain is transient in nature).
5. Major amputations of the lower limbs.
6. Active diabetic foot ulcers.
7. Diagnosed malignancy.
8. Patient has a pacemaker, defibrillator or neurostimulator.
9. Pregnancy (see section 4.3)

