6.1 Identification

Recruitment will take place from NHS Trusts with PDPN services and their aligned primary care and podiatry services. As this study requires a device that cannot be moved to where the patient is, the device will be placed centrally in the research centre and all patients whether recruited from primary or secondary care will receive the treatment in the research centre. A number of approaches will be taken to recruit participants:

1. Patients will be recruited from secondary care diabetes clinics, neuropathy clinics or pain clinics.
2. Working with the Clinical Research Network, patients will be recruited from primary care using GP registries. Identified GP practices will act as Participant Identification Centres (PICs) for the trial.
3. All currently planned centres have strong links with community podiatry services and this link will be used to identify appropriate patients. These services will act as PICs for the trial.
4. Once developed adverts will be put in outpatients in the NHS Trusts, primary care, and social media. As this material has not yet been developed it will be submitted as part of an amendment once the Regulatory approval have been obtained. Diabetes UK local patient groups will publicise the study. When social media is used, we will ensure that the information is clear that this is relevant to patients in certain locations.

NHS research staff may assist clinicians with caseload screening, use of electronic record searches or research registers/databases of existing patients (e.g. TriNetX) to help identify patients on their caseloads, according to local permissions as appropriate, for any of the methods described above.

All patients identified will receive a PIS and access to the online participant information tool. The online patient information tool has not yet been developed and will be submitted as an amendment once the Regulatory approval has been obtained. Patients will either give consent for the screening process at site or will receive a link to the screening consent to collect the pain scores over 7 days and access the participant's medical notes to assess study eligibility (see section 5.1). This will contain details of the study team to contact for further information. Advertising materials, once developed, will also contain contact details for further information.

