The study team will endeavour to recruit patients from a diverse population based on gender at birth, social deprivation and ethnicity. This should be possible considering that PDPN is strongly associated with socioeconomic disadvantage and is more common in South Asians compared to White Europeans [71, 72]. Some of the trial centres are well experienced in recruiting patients from ethnic minorities, such as Kings College Hospital which has a large Afro-Caribbean population in the foot clinic and Birmingham which has a large South Asian population in the neuropathy and foot clinics. We will also approach the South Asian Health Foundation to publicise the study. Recruitment from primary care and working with the local patient groups will also allow us access to a larger more diverse population than relying on recruitment from secondary care only. We will monitor recruitment and adapt strategies accordingly if needed.

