6.5 Blinding

The FREMS device used in this study will deliver both FREMS and TENS interventions. It is operated by inserting a numbered key card pre-programmed by the supplier with the randomised allocation. At randomisation each participant will be allocated a unique key card number by the randomisation database to be used only for that participant. The administering team will follow the same procedure for all participants administering the intervention in terms of electrodes positioning and setting the electrical dose. Patients will be instructed not to consider any perception at the site of electrode placement during the treatment as a sign of active treatment and also not to judge the absence of any such perception as a sign of sham treatment, similar to previous RCTs [43, 44] as current perception varies according to the severity of the neuropathy and the site of the electrode [73, 74]. Using TENS will allow patients who still have remaining sensation to feel the “buzzing” which is also felt by delivering FREMS. These measures will ensure blinding of the delivery team, investigators and participants as both treatments will be delivered in the same way via the same machine and participants will feel electrical buzzing in both treatments.

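### Patients who have already had FREMS are not excluded, so some participants may recognise their allocation in a sham-controlled trial with a self-reported primary outcome

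*Protocol*

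**What the plan says.** Section 4.2 has nine exclusion criteria, repeated in the Trial Summary. Those that concern electrical stimulation are "Currently using TENS for PDPN" and an implanted pacemaker, defibrillator or neurostimulator. In section 4.1 the criterion on earlier treatment concerns drugs only: "Have tried at least two drugs from two different classes for PDPN". Previous FREMS appears in neither list, and past TENS use is not addressed.

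The protocol also shows that FREMS-treated patients exist:

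- Section 1.5.4 describes a neuropathy clinic at a Birmingham hospital that offered FREMS to "Patients with PDPN (N=23) who failed to respond to (or did not tolerate) at least two lines of pharmacotherapy".
- Section 6.1 states that "Patients will be recruited from secondary care diabetes clinics, neuropathy clinics or pain clinics". Among centres experienced in recruiting ethnic minorities it names "Birmingham which has a large South Asian population in the neuropathy and foot clinics".
- Section 1.7 reports that "patients contact us asking for another FREMS treatment session 4-6 months after their initial treatment".

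On blinding, section 6.5 relies on one machine, one procedure and the statement that "participants will feel electrical buzzing in both treatments". Section 1.5.1 describes TENS as fixed in frequency and FREMS as modulated in both frequency and pulse duration.

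**The concern.** Table 1 in section 1.2 presents credible blinding as a main advance over the earlier FREMS trials, whose control arms received no current, so that sensation could reveal the allocation. Giving both arms a perceptible current addresses this for patients who have never had FREMS. It is less secure for someone who has been through a course of 10 sessions and has a remembered sensation to compare with.

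The primary outcome is the participant's own pain rating. Someone who recognises FREMS may rate pain lower through expectation, and someone who recognises the sham may rate it higher through disappointment. Both would push the difference in favour of FREMS. The direction is an inference, but it is the usual one for a self-reported outcome.

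Eligibility is fixed in the protocol, so a statistical analysis plan would not be expected to close this gap.

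**Working it through.** **1. Is such a patient eligible as the criteria stand?** Take someone treated with FREMS earlier whose pain has returned. Nothing in section 4.1 or 4.2 bars entry on that ground. Section 1.5.4 gives a mean NRS at 3 months after treatment of 6.2 (SD 3.0), so many treated patients would still meet the threshold of 4.

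**2. Does anything else deal with it?** The minimisation factors in section 6.4.2 are centre, age, gender at birth, diabetes type, ethnicity and opioid use. Previous FREMS is not among them. The baseline items listed in section 9 (Visit 0) do not name it. Perceived treatment arm (section 8.4.1, item 11) may detect unblinding but cannot prevent it.

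**3. The plan's own sample size.** Inputs from section 14.1: difference 0.6, SD 1.65, two-sided 5%, power 90%, attrition 10%.

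- Normal approximation: n = 2 × (1.960 + 1.282)² × 1.65² / 0.6² = 158.9, so 159 per group.
- Two-sample t-test: 159.9, so 160 per group and 320 in total.
- Attrition: 320 / 0.90 = 355.6, so 356.

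The stated 160 per group and 356 in total reproduce and are not in dispute.

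**4. Possible bias from recognition.** The protocol gives no expected number of FREMS-experienced participants, so this is an illustration. Let f be their share, taken as equal in both arms and among those analysed. Let b be the between-arm difference that recognition alone creates among them. Then:

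- overall bias = f × b
- SE of the difference with 160 analysed per arm = 1.65 × √(2/160) = 0.184
- two-sided type I error = Φ(bias/SE − 1.96) + Φ(−bias/SE − 1.96)

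The range for b, 0.6 to 2.0 points, is an assumption. The limiting case for f is all 23 clinic patients: 23/356 = 6.5%. A case with about half of them, 12/356 = 3.4%, is shown beside it.

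| Previously treated | f | b | Bias (points) | Type I error |
|---|---|---|---|---|
| 12 | 3.4% | 0.6 | 0.02 | 5.1% |
| 12 | 3.4% | 2.0 | 0.07 | 6.5% |
| 23 | 6.5% | 0.6 | 0.04 | 5.5% |
| 23 | 6.5% | 1.0 | 0.06 | 6.4% |
| 23 | 6.5% | 2.0 | 0.13 | 10.8% |

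For the last row, 0.129/0.184 = 0.70, and Φ(−1.26) + Φ(−2.66) = 0.104 + 0.004 = 0.108.

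**The case against.** The strongest reply is that the numbers are small and recognition is unproven. For 6.5%, nearly everyone treated at one clinic would have to return, meet every criterion again and accept an even chance of TENS. Section 7.6 says that FREMS is not generally available in the NHS. Section 6.5 tells patients not to read any sensation, or its absence, as a sign of allocation, and notes that perception varies with neuropathy severity and electrode site. Section 7.1 sets the current at each electrode to what the patient can feel without discomfort. Nothing in the protocol shows that neuropathic patients can tell the two pulse patterns apart months or years later. Section 6.1 says Birmingham without naming the hospital, so that it means the same clinic is an inference.

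All of this stands as an argument about size. It does not close the gap. The instruction to patients does not remove a remembered sensation, and limited availability also makes the trial an obvious route to a repeat course.

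A reader might infer more than the protocol supports, in four ways:

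- **Enrichment with known responders.** Section 1.7 gives no number, site or response status for those asking for repeats. That they benefited is plausible but undocumented. Under 1:1 randomisation, a truly larger effect in them would change whom the result applies to; it would not create a spurious difference.
- **Residual benefit at baseline.** Randomisation would be expected to balance it across arms. Entry requires a current 7-day mean of at least 4, and section 14.2 adjusts for baseline where possible. It would not bias the randomised contrast.
- **Adding the pilot trial's patients.** With roughly half of its 25 patients on FREMS (assumption), the pool would be about 36, or 10% of 356. But section 1.5.6 places the pilot in Nuneaton, which the protocol does not name as a trial site.
- **A shift of up to a fifth of the 0.6-point target.** That is 0.12 of 0.6, or 20%. It needs near-total re-enrolment together with a 2-point effect for which the protocol offers no source.

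**Conclusion.** The omission is a fact, and it weakens the feature on which the trial rests its claim to better evidence. Followed as written, the plan can admit participants who already know the active stimulus into a sham comparison judged by their own pain scores. Unblinding is the route to bias.

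The size is uncertain and probably modest. At the limit of all 23 clinic patients, the bias is 0.04 to 0.13 points against a target of 0.6, with type I error of about 5.5% to 11%; a figure at or below the lower end is more likely. This rests on three assumptions: that the clinic in section 1.5.4 is among the recruiting clinics, that previously treated patients can recognise the stimulus, and that recognition creates 0.6 to 2.0 points among them. The sample size is not affected.

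**What to change.** Add *Any previous FREMS treatment* to section 4.2 and to the matching list in the Trial Summary. Record past TENS use at baseline, because only current use is excluded, so that perceived treatment arm at the end of treatment can be summarised by it.

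If previously treated patients have already been randomised, keep them in the intention-to-treat analysis, record their previous exposure, and repeat the primary analysis without them as a sensitivity analysis.

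The cost is a protocol amendment, one baseline question and the loss of a few candidates, since FREMS is not generally available outside the trial.
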